10.3.2.2 Assessment of Shift from Baseline in Clinical Laboratory Variables

The baseline and post-baseline laboratory observations will be categorized as Grade 0, Grade 1, Grade 2, Grade 3, and Grade 4 and shifts from baseline grade to worst ontherapy grade will be summarized. Toxicity grading scale is based on National Cancer Institute Common Toxicity Criteria (NCI CTC) AE version 4.03. Shift tables from Baseline according to the grades will be provided for laboratory variables.

For LDL cholesterol, HDL cholesterol, total cholesterol, and triglycerides, the following categories according to National Cholesterol Education Program (NCEP) Adult Treatment Panel III (ATP III) guidelines will be used.

- LDL cholesterol ($< 3.36, \ge 3.36 \text{ and } < 4.14, \ge 4.14 \text{ mmol/L}$)
- HDL cholesterol ($< 1.03, \ge 1.03 \text{ mmol/L}$)
- Total cholesterol ($< 5.17, \ge 5.17 \text{ and } < 6.21, \ge 6.21 \text{ mmol/L}$)
- Triglycerides ($< 1.69, \ge 1.69 \text{ and } < 2.26, \ge 2.26 \text{ mmol/L}$)

Note that the minimum/maximum category is used, rather than the category of the minimum/maximum value. The two may be different due to variation in the reference range.

No statistical tests will be performed for this analysis.

10.3.2.3 Assessment of Potentially Clinical Significant Laboratory Values

The criteria for potentially clinically significant laboratory values will be determined by CTCAE criteria of Grade 2, Grade 3, Grade 4 and ≥ Grade 3(if applicable), with a grade worsening compared to baseline. Toxicity grading scale is based on National Cancer Institute Common Toxicity Criteria (NCI CTC) AE version 4.03. The number and percentage of subjects meeting the criteria for potentially clinically significant laboratory values will be summarized by treatment groups.

10.3.2.4 Assessment of Liver Elevations

According to FDA's Guidance for Industry "Drug-Induced Liver Injury: Premarketing clinical evaluation" (July 2009), when aminotransferase (AT) abnormalities indicating hepatocellular injury are accompanied by evidence of impaired hepatic function (bilirubin elevation > 2 × ULN), in the absence of evidence of biliary obstruction (i.e., significant elevation of ALP) or some other explanation of the injury (e.g., viral hepatitis, alcohol hepatitis), the combined finding (i.e., Hy's Law cases) represents a signal of a potential for the drug to cause severe DILI.

For the purpose of assessing for potential Hy's law cases, the frequencies and percentages of subjects with post baseline liver specific function test values that meet the following criteria of potential clinical interest will be summarized by treatment groups:

- ALT \geq 3 × ULN
- ALT \geq 5 × ULN
- ALT $\geq 10 \times ULN$
- ALT $\geq 20 \times ULN$
- AST \geq 3 × ULN
- AST \geq 5 × ULN
- AST $> 10 \times ULN$

- $AST > 20 \times ULN$
- TBL \geq 2 × ULN
- Alkaline phosphatase $\geq 1.5 \times ULN$
- ALT and/or AST \geq 3 × ULN and concurrent TBL \geq 1.5 × ULN
- ALT and/or AST \geq 3 × ULN and concurrent TBL \geq 2 × ULN

10.3.3 **Analysis of Long-Term Laboratory Data**

10.3.3.1 **Assessment of Clinical Laboratory Variables**

[figure not shown]
Analyses of hematology, chemistry, and urinalysis variables which are measured longitudinally will be performed by visits and by treatment group sequences as described in Section 10.1. For each analysis, the following summary statistics of visit values will be presented for each treatment group sequence: sample size, mean, standard deviation, minimum, median and maximum.

Analyses will be performed for change from baseline in hemoglobin, lymphocytes, neutrophils, creatinine, and creatine phosphokinase (CPK).

Descriptive summary by visit or mean change from baseline in laboratory values for subjects who switched from upadacitinib 30 mg QD to 15 mg QD will be censored at the time of dose switch, and descriptive summary by visit or mean change from baseline for values post switch will be summarized separately, as described in Section 10.1.

10.3.3.2 **Assessment of Potentially Clinical Significant Laboratory Values**

Long-term laboratory data will be summarized based on the number and percentage of subjects meeting the criteria for potentially clinical significant laboratory values and by the actual treatment received at the time of the event occurrence. The treatment groups for summarizing potentially clinically significant laboratory values are the same as the ones for long-term AE analysis as described in Section 8.1.

A subject can be counted under different treatment groups if he/she was on placebo from baseline to Week 24 and then started upadacitinib 15 or 30 mg at Week 24 and experienced potentially clinical significant laboratory values under different treatment groups.

[figure not shown]
In the evaluation of potentially clinically significant laboratory values, the baseline value will be determined by the last non-missing measurement recorded on or before the date of the first dose of study drug in the corresponding treatment group (which may be different than the first dose of study drug received in the study). For example, for a subject who started on placebo and switched to upadacitinib 15 mg QD at Week 24, lab values under upadacitinib 15 mg QD exposure would be evaluated against the baseline value defined as the last non-missing measurement recorded on or before the date of the first dose of upadacitinib 15 mg QD. For subjects who switched from upadacitinib 30 mg QD to upadacitinib 15 mg QD, lab values under upadacitinib 15 mg QD exposure would still be evaluated against the baseline defined based on the first dose of Upadacitinib 30 mg QD.

A listing of all subjects with any laboratory determination meeting CTCAE criteria of Grade 3 or above with a grade worsening compared to baseline will be provided. For each of these subjects, the whole course of the respective parameter will be listed.

10.3.3.3 Assessment of Liver Elevations

The frequencies and percentages of subjects with post-baseline liver-specific function test values that meet the following criteria of potential clinical interest will be summarized by the actual treatment received at the time of the event occurrence. The treatment groups for summarizing liver elevations are the same as the ones for long-term AE analysis as described in Section 8.1.

A subject can be counted under different treatment groups if he/she was on placebo from baseline to Week 24 and then started upadacitinib 15 or 30 mg at Week 24 and experienced potentially clinical significant laboratory values under different treatment groups.

A listing of potentially clinically significant liver elevations based on criteria specified above will be provided. For each of these subjects, the whole course of the respective parameter will be listed.

10.4 Analysis of Vital Signs

10.4.1 Variables and Criteria Defining Abnormality

Vital sign variables include sitting systolic blood pressure, sitting diastolic blood pressure, pulse rate, and weight. The criteria for potentially clinically significant vital sign findings are presented in Table 13.

[figure not shown]
Table 13. Criteria for Potentially Clinically Significant Vital Sign Findings

Vital Sign	Category	Criteria for Potential Clinically Significant Vital Signs
Systolic blood pressure	Low	Value ≤ 90 mmHg and decrease ≥ 20 mmHg from Baseline
	High	Value ≥ 160 mmHg and increase ≥ 20 mmHg from Baseline
Diastolic blood pressure	Low	Value ≤ 50 mmHg and decrease ≥ 10 mmHg from Baseline
	High	Value $\geq 100 \text{ mmHg}$ and increase $\geq 10 \text{ mmHg}$ from Baseline
Weight	High	> 7% increase from baseline
	Low	> 7% decrease from baseline

10.4.2 Analysis of Vital Signs by Week 24

Analyses of vital sign variables which are measured longitudinally will be performed by visits and by the treatment groups of upadacitinib 15 mg QD, upadacitinib 30 mg QD, adalimumab 40 mg EOW, and the combined placebo group. For each analysis, the following summary statistics will be presented for each treatment group: sample size, mean, standard deviation, minimum, median, and maximum.

The number and percentage of subjects meeting the criteria for potentially clinically significant vital sign values will be summarized by treatment group.

10.4.3 Long-Term Analysis of Vital Signs

Analyses of vital signs variables which are measured longitudinally will be performed by visits and by treatment group sequences as described in Section 10.1. For each analysis, the following summary statistics will be presented for each treatment group: sample size, mean, standard deviation, minimum, median, and maximum.

Long-Term Vital Sign will also be summarized based on the number and percentage of subjects meeting the criteria for potentially clinical significant vital sign values and by the actual treatment received at the time of the event occurrence. The treatment groups are the same as the ones for long-term AE analysis as described in Section 10.2.2. A subject can be counted under different treatment groups if he/she was on placebo from baseline to Week 24 and then started upadacitinib 15 or 30 mg at Week 24 and experienced potentially clinical significant laboratory values under different treatment groups. In the evaluation of potentially clinically significant vital sign values, the baseline value will be determined by the last non-missing measurement recorded on or before the date of the first dose of study drug in the corresponding treatment group, similarly as described in Section 10.3.3.2.

Descriptive summary by visit in vital signs for subjects who switched from upadacitinib 30 mg QD to 15 mg QD will be censored at the time of dose switch, and descriptive summary by visit for values post switch will be summarized separately, as described in Section 10.1. The treatment groups for summarizing PCS vital sign values are the same as the ones for long-term AE analysis as described in Section 8.1. For the purpose of evaluating PCS vital sign values, for subjects who switched from upadacitinib 30 mg QD to upadacitinib 15 mg QD, baseline is defined based on the first dose of Upadacitinib 30 mg QD, similarly as described in Section 10.3.3.2.

A listing of all subjects with any vital sign values meeting the criteria for potentially clinically significant vital signs will be provided. For each of these subjects, the whole course of the respective parameter will be listed.

11.0 Summary of Changes

11.1 Summary of Changes between the Previous Version and the Current Version

The primary efficacy analysis has been completed under the SAP version 3.0 and SPP 1.0, Period 1 reporting has been completed under the SAP version 3.0 and SPP version 2.0. The current SAP update applies only to future reporting of long-term analysis.

- 1. Updated throughout the SAP to align with Protocol Amendment 6.01 and Amendment 7 and 7.01, including handling of dose switch from upadacitinib 30 mg QD to 15 mg QD (hereafter referred to as "dose switch").
 - a. Updated Section 7.0 and Section 8.1 to provide analysis details that incorporate dose switch.
 - b. Updated Section 9.1.1 to summarize the analysis changes that incorporate dose switch for long-term efficacy analysis.
 - c. Updated Section 10.1, Section 10.2.2, Section 10.3.3.1, Section 10.3.3.2, Section 10.3.3.3 and Section 10.4.3 to incorporate handling of dose switch for long-term safety analysis.
- 2. Updated Section 9.1.2 and Section 9.3 for long-term binary endpoint analysis for Week 104 and future analyses.
 - a. Updated Section 9.1.2 to describe the missing data handling approach for the additional long-term efficacy analysis using MMRM/GLMM models.
 - b. Updated Section 9.3 to add NRI and/or GLMM for long-term non-radiographic binary endpoint analysis (Week 104 and future).
 - c. Updated Section 9.3 to add MMRM based on AO data for long-term continuous endpoint analysis, including radiographic continuous endpoints (Week 104 and future).

- 3. Updated language in Section 10.1, Section 10.2.1.1, Section 10.2.2.1, Section 10.2.2.3 to add clarity for safety analysis.
- 4. Updated Section 10.2.1.6 and Section 10.4.1 to align with the latest upadacitinib AESI definitions in PSSAP V4.0.
- 5. Added Appendix E to describe analysis accounting for impact of COVID-19 pandemic.

[figure not shown]
12.0 Version History

Table 14. SAP Version History Summary

Version	Date	Summary
1.0	12 Apr 2018	Original version submitted to FDA for feedback.
2.0	12 Dec 2018	Revised by adding estimand for the primary and ranked secondary endpoints based on FDA's feedback.
3.0	12 Dec 2019	This version was approved and submitted to FDA prior to Week 24 DBL and unblinding. Endpoints were revised as part of Protocol Amendment 4; Revised tipping point analysis for the primary endpoints based on FDA's feedback.
4.0	08 Jul 2021	Incorporating update 1) in the study duration from 3 to 5 years in protocol amendment 6.0; 2) in statistical analysis to handle the missing data due to COVID-19; 3) in wording changes in PSSAP; 4) in handling of dose switch from upadacitinib 30 mg QD to 15 mg QD; 5) Add additional long-term analysis method for Week 104 and future visits.

Appendix A. SAS Procedure for Mantel-Haenszel Test

A SAS procedure, the Proc Freq, will be used to compute the statistics using the Mantel-Haenszel method.² Risk difference, 95% CI and p value will be provided through the program.

SAS code example:

```
title 'Placebo vs ABT-494 30 mg QD';
proc freq data= wk12_nri;
where TRTP='Placebo'|TRTP='ABT-494 30 mg QD';
table TRTP*aval/ nopercent nocol chisq riskdiff(cl=wald)
alpha=0.05;
run;

title2 'For p-values';
proc freq data=wk12_nri;
where TRTP='Placebo'|TRTP='ABT-494 30 mg QD';
tables DMARDBL*TRTP*aval/ cmh;
run;
```

[figure not shown]

Appendix B. Tipping Point Analysis for ACR20 at Week 12

To assess the robustness of the primary analysis using NRI data handling, tipping point analysis is conducted on the primary endpoint ACR20. The analysis is conducted on the FAS using As Observed data handling.

The tipping point analysis will be performed by multiple imputations using logistic regression, allowing the imputed ACR response rate to systematically vary from 0% to 100% in both upadacitinib and placebo, respectively. This will be accomplished by modifying the predicted probabilities for the responses through shifting the log odds ratios,⁴ then directly sampling the missing ACR20 response from the Bernoulli distribution with the modified probabilities.

For each pair of shift parameters, the same CMH method used for the primary endpoint will be performed on each of the multiple imputed datasets to obtain the results for each comparison of the upadacitinib treatment group versus the placebo group. Because chi-square distribution of CMH test statistic is skewed from the normal distribution, to combine the results from the CMH test using Rubin's method, a transformation will be conducted to normalize the CMH statistic.⁵ These transformed results will be then aggregated using Rubin's method to get *P*-values.

Appendix C. Three Arm Approach to Non-Inferiority (NI) Testing

[figure not shown]
Let parameters T, R and P represent the ACR20 response rates for an upadacitinib dose group, the adalimumab group, and the combined placebo group respectively and let n be the sample size per group (as all groups have an equal sample size). Let α denote the type 1 error rate and β denote the type 2 error rate (so 1- β is the test power). The null and alternative hypotheses of non-inferiority testing have the form:

$$H_0: T - R \le -(1 - \phi)(R - P)$$
 vs. $H_1: T - R > -(1 - \phi)(R - P)$.

 ϕ is a pre-specified fraction of reference drug effect to be retained by test drug, and it is set to be 50% in this NI comparison. Using the three-arm approach, both T-R and R-P are estimated from the current clinical trial. The three-arm approach test statistic has the following form:

$$Z = \frac{\bar{Y}_T - \bar{Y}_R + (1 - \phi)(\bar{Y}_R - \bar{Y}_P)}{\sqrt{\frac{\bar{Y}_T(1 - \bar{Y}_T)}{n} + \frac{\phi^2 \bar{Y}_R(1 - \bar{Y}_R)}{n} + \frac{(1 - \phi)^2 \bar{Y}_P(1 - \bar{Y}_P)}{n}}},$$

where \overline{Y}_T , \overline{Y}_R and \overline{Y}_P are the sample ACR20 response rates for the upadacitinib dose group, the adalimumab group, and the combined placebo group respectively. The null hypothesis is rejected at a two-sided α level if $Z > Z_{\alpha/2}$, where $Z_{\alpha/2}$ is the upper $\alpha/2$ percentile of the standard normal distribution.

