4.2 Overall Study Design and Plan

This is a Phase 3 multicenter study that includes two periods. Period 1 is 56 weeks in duration and includes a 24-week randomized, double-blind, parallel-group, placebocontrolled and active-comparator controlled period followed by an additional 32 weeks of blinded active comparator-controlled treatment (Weeks 24-56). Period 1 is designed to compare the safety, tolerability, and efficacy of upadacitinib 15 mg QD and 30 mg QD versus placebo and versus adalimumab 40 mg every other week (eow) in subjects with moderately to severely active PsA who have an inadequate response to non-biologic DMARDs (DMARD-IR). Period 1 is also designed to compare the efficacy of upadacitinib 15 mg QD and 30 mg QD versus placebo for the prevention of structural progression. Period 2 is an open-label (blinded until the last subject completes the last visit of Period 1), long-term extension of up to a total treatment duration of approximately 5 years to evaluate the safety, tolerability and efficacy of upadacitinib 15 mg QD and 30 mg QD in subjects with PsA who have completed Period 1. Starting with Amendment 6.01, subjects in Japan receiving upadacitinib 30 mg QD will be switched to upadacitinib 15 mg QD. For other countries, starting with Amendment 7 and 7.01, subjects receiving upadacitinib 30 mg QD will be switched to upadacitinib 15 mg QD.

The study is designed to enroll approximately 1640 subjects at approximately 350 study centers worldwide to meet scientific and regulatory objectives without enrolling an undue number of subjects in alignment with ethical considerations.

[figure not shown]
The study duration will include a 35-day screening period; a 56-week blinded period which includes 24 weeks of double-blind, placebo-controlled and active comparator-controlled treatment followed by 32 weeks of active comparator-controlled treatment (Period 1); a long-term extension period of up to a total treatment duration of approximately 5 years ([blinded to sites and investigators until the last subject completes the last visit of Period 1] Period 2); and a 30-day follow-up call or visit; and a 70-day follow-up call. Subjects who meet eligibility criteria will be randomized in a 2:2:2:1:1 ratio using an Interactive Response Technology (IRT) to receive double-blind study drug in one of the following treatment groups:

- Group 1: Upadacitinib 15 mg QD, N = 410 (Day 1 to Week 24) → Upadacitinib 15 mg QD (Week 24 and thereafter)

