- Group 2: Upadacitinib 30 mg QD, N = 410 (Day 1 to Week 24) → Upadacitinib 30 mg QD (Week 24 and thereafter)
- Group 3: Adalimumab (40 mg eow) (N = 410)
- Group 4: Placebo, N = 205 (Day 1 to Week 24) → Upadacitinib 15 mg QD (Week 24 and thereafter)
- Group 5: Placebo, N = 205 (Day 1 to Week 24) → Upadacitinib 30 mg QD (Week 24 and thereafter)

Randomization will be stratified by extent of psoriasis (\geq 3% body surface area [BSA] or < 3% BSA), current use of at least 1 DMARD (Yes or No), presence of dactylitis, and presence of enthesitis, except for subjects from China and Japan, for which randomization will be stratified by extent of psoriasis (\geq 3% body surface area [BSA] or < 3% BSA) only. See Section 5.5.3 of protocol for details.

A schematic of the overall study design is shown in Figure 1 below.

Figure 1. Study Design

- a. All subjects will receive x-rays of hands and feet at Screening, Wk 24, Wk 56, Wk 104, Wk152, and Wk 260/PD.
- b. At Week 16 rescue therapy will be offered to subjects classified as non-responders (defined as not achieving at least 20% improvement in either or both tender joint count (TJC) and swollen joint count (SJC) at both Week 12 and Week 16) as described in Protocol Section 5.2.3.4.
- c. At Week 24, all placebo subjects will switch to Upadacitinib 15 mg QD or 30 mg QD (1:1 ratio) regardless of response.

Note: For subjects in Japan only: Upon approval of protocol amendment 6.01, subjects receiving upadacitinib 30 mg QD will be switched to upadacitinib 15 mg QD prior to marketing approval in Japan for the treatment of psoriatic arthritis.

Note: Upon approval of protocol amendment 7 and 7.01, subjects receiving upadacitinib 30 mg QD will be switched to upadacitinib 15 mg QD at their next scheduled study visit in other countries.

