Psoriasis Area Severity Index (PASI) 75 response at Week 16	Subjects with \geq 3% BSA psoriasis at baseline are included in the analysis
Proportion of subjects with resolution of enthesitis (LEI = 0) at Week 24	Subjects with baseline LEI > 0 are included in the analysis
Proportion of subjects with resolution of dactylitis at Week 24	Subjects with baseline LDI > 0 are included in the analysis

For MDA at Week 24, resolution of enthesitis at Week 24 and resolution of dactylitis at Week 24, in addition to the NRI data handling as defined in Section 9.1.2, subjects who meet the rescue criteria (i.e., not achieving at least 20% improvement in either or both tender joint count (TJC) and swollen joint count (SJC) at both Week 12 and Week 16) will also be treated as non-responders. The corresponding primary estimand is the difference in the proportion of patients who achieved MDA/resolution of enthesitis/resolution of dactylitis at Week 24, and who did not discontinue study drug and did not initiate rescue therapy by Week 24. The comparison is for each upadacitinib dose group vs placebo for patients randomized and treated with at least one dose of study drug. NRI data handling will be used to analyze the primary estimand for binary endpoints.

Supplementary analysis using AO data handling will also be conducted. The corresponding supplementary estimand is the same as defined in Section 9.2.2 except for the definition of the efficacy measurement.

[figure not shown]
Point estimate and 95% CI using normal approximation will be provided for the response rate for each randomized treatment group. Treatment comparisons will be made between each upadacitinib dose and the combined placebo group using the Cochran-Mantel-Haenszel test (refer to Appendix A). The CMH test adjusts for the main stratification factor of current DMARD use (yes/no). Point estimate, 95% CI using normal approximation and the p-value for the treatment difference will be presented.

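### The Appendix C non-inferiority test omits current DMARD use, a randomisation factor adjusted for elsewhere; it is valid but gives up a little precision

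*SAP*

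**What the plan says.** SAP Appendix C defines the non-inferiority statistic from the three sample ACR20 rates: upadacitinib dose (T), adalimumab (R) and combined placebo (P). Of the retained fraction it says "it is set to be 50% in this NI comparison". The variance has one n, justified by "as all groups have an equal sample size", and no stratification term. SAP 9.2.3 places this test seventh among the ranked key secondary endpoints.

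Current DMARD use is handled differently elsewhere:
- SAP 4.2 and Protocol 5.5.3 make it a randomisation stratifier, except in China and Japan.
- SAP 9.2.1 adjusts the primary ACR20 test for it.
- SAP 9.2.3 says of the ranked binary endpoints versus placebo: "The CMH test adjusts for the main stratification factor of current DMARD use (yes/no".
- The MMRM in SAP 9.1.2 and 9.2.3 includes it, and the same model serves the ranked pain and HAQ-DI comparisons with adalimumab.
- SAP 9.2.4 adjusts the additional binary comparisons for it, against adalimumab as well as placebo.

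SAP 4.3 claims at least 85% power for this test, at two-sided 0.025 and allowing for 10% dropout.

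**The concern.** When randomisation is stratified on a factor related to response, a variance built from crude proportions keeps the between-stratum component that the design has already balanced out. The standard error is then a little too large and the test a little less likely to succeed. The factor is recorded for every subject and used in the neighbouring analyses, so leaving it out gives up precision for nothing.

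The place where this happens matters somewhat. Rank 7 comes before ranks 8 to 14 in the stated order, and ACR20 superiority over adalimumab is expressly conditional on it. The test also has little power to spare.

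**Working it through.** **Inputs.** ACR20 rates T = 0.50, R = 0.50, P = 0.30 (SAP 4.3). Retained fraction 0.5 (Appendix C). Planned n of 410 per arm, with placebo 205 + 205 (SAP 4.2). With 10% dropout, n = 0.9 × 410 = 369. Levels: two-sided 0.025 for the power statement (critical value 2.241), and 0.0499/2 = 0.02495 per dose for testing (SAP 9.2.5; critical value 2.242). I assume that a dose's full starting level reaches rank 7, because the transfer weights in Figure 2 are not available.

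**Step 1: the plan's own figure.** The contrast is T − 0.5R − 0.5P = 0.50 − 0.25 − 0.15 = 0.10. Its variance times n is 0.25 + 0.25 × 0.25 + 0.25 × 0.21 = 0.25 + 0.0625 + 0.0525 = 0.365.
- n = 369: SE = √(0.365/369) = 0.03145; 0.10/SE = 3.180; power = Φ(3.180 − 2.241) = 82.6%.
- n = 410: SE = 0.02984; 0.10/SE = 3.352; power = 86.7%.

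The stated 85% is therefore met without dropout but not with it. I use n = 369 below because it reproduces the plan's SHS power (90.2% against approximately 90%). Moving from 0.025 to 0.02495 leaves 82.6% unchanged to one decimal.

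**Step 2: stratify by DMARD use.** Let w be the share in the smaller stratum and d the difference in response between strata, taken as the same in all arms. Each arm's variance p(1 − p) falls by b = w(1 − w)d². The contrast variance falls by (1 + 0.25 + 0.25)b = 1.5b. The documents give neither w nor d, so the rows below are an assumed range. Power is at 0.02495 and n = 369.

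| w | d | b | 0.365 − 1.5b | Cut | SE | Power |
|---|---|---|---|---|---|---|
| 20% | 10 points | 0.0016 | 0.3626 | 0.7% | 0.03135 | 82.8% |
| 50% | 20 points | 0.0100 | 0.3500 | 4.1% | 0.03080 | 84.3% |

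Stratified randomisation already makes the crude contrast a little less variable than 0.365/n. The true power of the unstratified test is therefore slightly above 82.6%, and the gain from stratifying is, if anything, smaller than the table suggests.

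**Step 3: direction of the error.** The unstratified SE is too large by √(0.365/0.3626) = 1.003 to √(0.365/0.350) = 1.021, that is 0.3% to 2.1%. The one-sided error at nominal 0.0125 becomes about 0.0123 to 0.0110, which is conservative.

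**Step 4: the single n.** At 410/410/410 the common-n and arm-specific SEs are the same, 0.02984. If realised arms departed from their average by 2% or 5% (again assumptions), a common average n would misstate the SE by at most 0.7% or 1.9%, in either direction.

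**The case against.** The best case against the point is that nothing is wrong with the test. It is valid, it errs on the safe side, and the equal-size remark is true of the design. The gain rests on strata that the documents do not describe. All of that stands, and it limits the point to efficiency.

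Four stronger readings are tempting, and the documents do not support them.
- A reader might infer that every other ranked ACR20 comparison is stratified. The CMH sentence in SAP 9.2.3 covers comparisons with placebo. Superiority over adalimumab (rank 10) has no stated statistic, and SAP 9.2.5 supplies none. In Appendix A only the p-value step includes DMARD use; the risk difference and its interval do not.
- A reader might infer that the single n makes the standard error wrong. It is exact at plan. The Full Analysis Set loses only subjects who were never dosed, and later dropouts stay in as non-responders, so dropout does not unbalance the arms.
- A reader might attribute the shortfall against 85% to the missing stratification. It arises from applying the 10% dropout, and even the most favourable row above stays below 85%.
- A reader might infer that precision lost here is lost for each of ranks 8 to 14. The stated order puts rank 7 first, but the arrows in Figure 2 are not available and SAP 9.2.5 also provides for transfer between doses.

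Timing is also a fair objection. SAP 11.1 says the primary efficacy analysis was completed under version 3.0 and that version 4.0 applies only to later long-term reporting. What survives is that a factor already collected and used in the neighbouring analyses was left out of this one.

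**Conclusion.** The point holds as a small, free improvement. The unstratified test controls its error rate and is slightly conservative. Under the assumed strata (20-50% in the smaller one, a 10-20 point difference in response, common to all arms), stratifying would reduce the contrast variance by about 0.7-4.1% and lift power at n = 369 from 82.6% to about 82.8-84.3%. With weaker strata the gain approaches zero. It does not by itself restore the stated 85%, which is a separate matter. The single n is a question of notation only.

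**What to change.** Within each current-DMARD-use stratum k, estimate T − 0.5R − 0.5P. Combine the strata with one pre-specified set of weights w_k common to all three arms, for example the pooled stratum proportions. Pairwise Mantel-Haenszel weights depend on two arm sizes and do not carry over directly to a three-arm contrast. Write the variance as the sum over k of w_k² × [p_Tk(1 − p_Tk)/n_Tk + 0.25 p_Rk(1 − p_Rk)/n_Rk + 0.25 p_Pk(1 − p_Pk)/n_Pk], which also disposes of the common n. Subjects in China and Japan were not stratified on this factor at randomisation, but it is recorded at baseline, so they can be placed in a stratum.

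Before unblinding this would cost a few lines of SAP text and code, with no extra subjects or data. For this trial the Week 12 test is done, so the Appendix C result should stand as the confirmatory one. The stratified contrast can be reported beside it as a labelled sensitivity analysis, with a note of which n was used.
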